3.8 OFF TREATMENT EVALUATIONS (FOLLOWING TREATMENT)

3.8.1 3 months

- Physical exam including ECOG status
- CBC with differential
- Chemistries: Sodium (Na), Potassium (K), Chloride (Cl), Total CO₂ (bicarbonate), Creatinine, Glucose, Urea nitrogen (BUN), Albumin, Calcium total, Alkaline Phosphatase, ALT/GPT, AST/GOT, Total Bilirubin, Total Protein
- CT scan of the chest, abdomen and pelvis (CT C/A/P) or MRI

3.8.2 6 months

- Physical exam including ECOG status
- CBC with differential
- Chemistries: Sodium (Na), Potassium (K), Chloride (Cl), Total CO₂ (bicarbonate), Creatinine, Glucose, Urea nitrogen (BUN), Albumin, Calcium total, Alkaline Phosphatase, ALT/GPT, AST/GOT, Total Bilirubin, Total Protein
- 12L ECG
- CT scan of the chest, abdomen and pelvis (CT C/A/P) or MRI

3.8.3 12 months

- Physical exam including ECOG status
- CBC with differential
- Chemistries: Sodium (Na), Potassium (K), Chloride (Cl), Total CO2 (bicarbonate), Creatinine, Glucose, Urea nitrogen (BUN), Albumin, Calcium total, Alkaline Phosphatase, ALT/GPT, AST/GOT, Total Bilirubin, Total Protein
- CT scan of the chest, abdomen and pelvis (CT C/A/P) or MRI

3.8.4 Following the 12-month evaluation patients will be followed via phone or e-mail contact every 6 months for survival

3.9 CRITERIA FOR REMOVAL FROM PROTOCOL THERAPY AND OFF STUDY CRITERIA

Prior to documenting removal off study, effort must be made to have all subjects complete a safety visit approximately 30 days following the last dose of study therapy. The following evaluation will occur:

- Physical exam including ECOG status
- CBC with differential
- Chemistries: Sodium (Na), Potassium (K), Chloride (Cl), Total CO2 (bicarbonate), Creatinine, Glucose, Urea nitrogen (BUN), Albumin, Calcium total, Alkaline Phosphatase, ALT/GPT, AST/GOT, Total Bilirubin, Total Protein
- CT scan of the chest, abdomen and pelvis (CT C/A/P) or MRI

3.9.1 Off Treatment Criteria

- Progressive Disease
- Excessive toxicity as defined in section **3.3**
- Allergic reaction to investigational agent
- The subject becomes pregnant
- PI discretion
- Patient request to be withdrawn from study

3.9.2 Off-study Criteria

- Death
- Patient request to be withdrawn from study
- PI discretion
- Investigator decision to the end the study

3.9.3 Off Protocol Therapy and Off-Study Procedure

Authorized staff must notify Central Registration Office (CRO) when a subject is taken protocol therapy and when a subject is taken off-study. A Participant Status Updates Form from the web site (<http://home.ccr.cancer.gov/intra/eligibility/welcome.htm>) main page must be completed and sent via encrypted email to: NCI Central Registration Office [contact].

4 SUPPORTIVE CARE

Appropriate supportive care for any side effects or toxicity may be provided by the Endocrine Oncology Branch. Patients may be admitted as necessary to manage issues related to study medication or disease process. Antidiarrheal treatment (e.g., loperamide) will be administered immediately upon the first onset of symptoms. Each subject will be instructed to have loperamide or a comparable anti-diarrheal medication readily available and to begin treatment for diarrhea at the first episode of poorly formed or loose stools or the earliest onset of bowel movements more frequent than normally expected for the subject until diarrhea free. Subjects will be instructed to notify the Investigator if diarrhea occurs and will be evaluated in the clinic for significant dehydration, possible electrolyte imbalance, and/or ongoing losses. If clinically significant dehydration is present, rehydration and electrolyte repletion will be performed. Additionally, subjects will be monitored following rehydration for the risk of recurrence and electrolyte imbalances and advised regarding appropriate fluid management to reduce the likelihood of subsequent dehydration events. Antiemetics will be given prophylactically after the first episode of nausea or vomiting. Growth factor support will be permitted for neutropenia or neutropenic fever.

5 BIOSPECIMEN COLLECTION

Test/assay	Samples	Type of tube	Collection time point	Location of specimen analysis
Direct Sanger Sequencing (for mutations in Table 1) and Immunohistochemistry for pERK, pAKT, pS6, HDAC2, survivin.	Tumor tissue sample from biopsy and or archival paraffin block.	Saline	Baseline (within 1 month prior to treatment)	Endocrine Oncology Branch Lab

5.1.1 Direct Sanger Sequencing and Immunohistochemistry

- An ultrasound -guided tumor biopsy will be obtained at baseline if the site of disease is readily accessible without posing a significant risk to the patient. If a tumor biopsy cannot be performed archival paraffin tumor blocks will be used with core biopsy of the tumor sample for direct Sanger sequencing of the driver mutations listed in **Table 1** and for immunohistochemistry for proteins listed above.
- Biopsy samples will be collected, placed on ice and sent immediately to the Endocrine Oncology Branch Laboratory.
- The direct Sanger sequencing and immunohistochemistry will be performed in the Endocrine Oncology Branch laboratory.

5.2 SAMPLE STORAGE, TRACKING AND DISPOSITION

Samples will be labeled with the date and time of acquisition, the type of tissue and patient study ID. Upon receipt in the lab, samples will be barcoded and logged into the tissue database, LabMatrix. Tissue will be stored in -20°C or -80°C freezers until molecular analysis and those for immunohistochemistry will be fixed in formalin. All freezers are monitored and are on separate emergency generator lines.

- All specimens obtained in the protocol are used as defined in the protocol. Any specimens that are remaining at the completion of the protocol will be stored in the conditions described below. The study will remain open so long as sample or data analysis continues. Samples from consenting subjects will be stored until they are no longer of scientific value or if a subject withdraws consent for their continued use, at which time they will be destroyed. The PI will report any loss or destruction of samples to the NCI IRB as soon as he is made aware of such loss.
- If the patient withdraws consent the participant's data will be excluded from future distributions, but data that have already been distributed for approved research use will not be able to be retrieved.

The PI will report destroyed samples to the IRB if samples become unsalvageable because of environmental factors (ex. broken freezer or lack of dry ice in a shipping container) or if a patient withdraws consent. Samples will also be reported as lost if they are lost in transit between facilities or misplaced by a researcher. Freezer problems, lost samples or other problems associated with samples will also be reported to the IRB, the NCI Clinical Director, and the office of the CCR, NCI.

6 DATA COLLECTION AND EVALUATION

6.1 DATA COLLECTION

Data will be collected using the NCI C3D web based data collection system.

The PI will be responsible for overseeing entry of data into an in-house password protected electronic system and ensuring data accuracy, consistency and timeliness. The principal investigator, associate investigators/research nurses and/or a contracted data manager will assist with the data management efforts. All data obtained during the conduct of the protocol will be kept in secure network drives or in approved alternative sites that comply with NIH security standards. Primary and final analyzed data will have identifiers so that research data can be attributed to an individual human subject participant.

End of study procedures: Data will be stored according to HHS, FDA regulations and NIH Intramural Records Retention Schedule as applicable.

Loss or destruction of data: Should we become aware that a major breach in our plan to protect subject confidentiality and trial data has occurred, the IRB will be notified.

6.2 ROUTINE DATA COLLECTION

6.2.1 Following enrollment, all adverse events will be described in the source documents and be reviewed by the designated research nurse, and captured in C3D.

6.2.2 During the follow up period (more than 30 days following the last treatment), only those events that are serious, unexpected, and related to the treatment will be captured in C3D.

6.2.3 Exclusions to Routine Data Collection:

The following Adverse Events will be captured only in the source documents and will not be reported in C3D:

- Laboratory values that do not support the diagnosis of a reportable event
- All grade 1 events

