3.3.2 Dose Delays and Discontinuation of CUDC-907

In the event that any of the above criteria are not met, study drug dosing will be held until the retreatment criteria are met. Treatment may then resume at the full dose of CUDC-907, as long as none of the criteria in **Table 4** and/or **Table 5** are met. Beyond Cycle 1, subjects held for > 7 days may restart treatment after the subject has met the above criteria at the discretion of the Investigator. Beyond Cycle 2, subjects may have study drug held for up for 1 full cycle (21 days). If beyond 1 full cycle, then the subject will be taken off treatment per section **4.9.2**.

Subjects who experience a DLT-like event will be either discontinued from further study treatment or their dose will be reduced as outlined in **Table 3**. A DLT-like event will be defined as any of the following AEs occurring at any time:

- Non-hematological \geq Grade 3 AE, other than Grade 3 nausea or Grade 3 vomiting in subjects treated with less than optimal antiemetic therapy.
- An AE resulting in a dose delay of 21 days.
- Grade 4 neutropenia \geq 7 days, or \geq Grade 3 neutropenia with fever > 101.3°F (38.5°C) or \geq Grade 3 neutropenia with infection.
- Grade 4 thrombocytopenia \geq 7 days, or \geq Grade 3 thrombocytopenia and significant bleeding.

Table 3 CUDC-907 Dose Reduction Steps

Reduction Steps:	Schedule	Dose
Starting dose	5/2	60 mg
Dose Reductions	Schedule	Dose
First dose reduction	4/3	60 mg
Second dose reduction	5/2	30 mg
Final dose reduction	4/3	30 mg

4/3 = 4 days on, 3 days off; 5/2 = 5 days on, 2 days off

Dose Adjustments for CUDC-907 Hematologic and Non-hematologic Toxicity

The administration of HDAC and PI3K inhibitors has been associated with predictable bone marrow suppression that is typically transient and reversible.

The administration of HDAC and PI3K inhibitors has also been associated with hyperglycemia. This hyperglycemia does not generally result in severe metabolic complications and typically resolves with therapeutic intervention. The treatment goal for glycemic control is fasting plasma glucose < 160 mg/dL; while making every attempt to avoid hypoglycemia. Dose modifications of CUDC-907 are based on the severity of toxicities.

CUDC-907 dose adjustments for hematologic and non-hematologic toxicities are shown in **Table 4** and **Table 5**.

Table 4 CUDC-907 Dose Adjustments for Hematologic and Non-Hematologic Toxicities			

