7 SAFETY REPORTING REQUIREMENTS/DATA AND SAFETY MONITORING PLAN

7.1 DEFINITIONS

7.1.1 Adverse Event

An adverse event is defined as any reaction, side effect, or untoward event that occurs during the course of the clinical trial associated with the use of a drug in humans, whether or not the event is considered related to the treatment or clinically significant. For this study, AEs will include events reported by the patient, as well as clinically significant abnormal findings on physical examination or laboratory evaluation. A new illness, symptom, sign or clinically significant laboratory abnormality or worsening of a pre-existing condition or abnormality is considered an AE. All AEs must be recorded on the AE case report form unless otherwise noted above in Section 6.2.

All AEs, including clinically significant abnormal findings on laboratory evaluations, regardless of severity, will be followed until return to baseline or stabilization of event. Serious adverse events that occur more than 30 days after the last administration of investigational agent/intervention and have an attribution of at least possibly related to the agent/intervention should be recorded and reported as per sections **7.3, 7.4**.

An abnormal laboratory value will be considered an AE if the laboratory abnormality is characterized by any of the following:

- Results in discontinuation from the study
- Is associated with clinical signs or symptoms
- Requires treatment or any other therapeutic intervention
- Is associated with death or another serious adverse event, including hospitalization.
- Is judged by the Investigator to be of significant clinical impact
- If any abnormal laboratory result is considered clinically significant, the investigator will provide details about the action taken with respect to the test drug and about the patient's outcome.

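### After day 30, Section 6.2.2 enters serious related events in C3D only if they are also unexpected, a narrower filter than the late SAE rule in 7.1.1, so the two sources will not match

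*Combined protocol and SAP*

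**What the plan says.** Section 6.1 names C3D as the system in which the trial's data are collected. Section 6.2.1 provides that after enrollment "all adverse events will be described in the source documents", reviewed by the research nurse and captured in C3D. Section 6.2.2 narrows this once more than 30 days have passed since the last treatment: "only those events that are serious, unexpected, and related to the treatment will be captured in C3D". The three conditions are joined, so an event must meet all of them.

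Section 7.1.1 makes two relevant statements. The first is general and gives way to Section 6.2: "All AEs must be recorded on the AE case report form unless otherwise noted above in Section 6.2". The second concerns the late window: "Serious adverse events that occur more than 30 days after the last administration of investigational agent/intervention" and that "have an attribution of at least possibly related to the agent/intervention should be recorded and reported as per sections" 7.3 and 7.4. It does not mention expectedness.

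Section 7.1.3 defines an unexpected event by reference to the investigator brochure: one that is not listed there, or is not listed at the specificity or severity observed. Section 7.3 sends serious events to the sponsor and expressly includes those the protocol or brochure already lists. Section 7.4 sends related serious events to the collaborator within 24 hours. Section 7.2.2 puts all serious events in the continuing-review table for the IRB.

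**The concern.** Expectedness is a criterion for deciding how urgently an event is reported. It is a poor criterion for deciding whether an event enters the dataset from which toxicity is summarized. Used in that way, it removes the late serious events that fit the drug's known profile and keeps those that do not.

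The protocol looks for late toxicity. Section 3.8 schedules blood counts and chemistries, including glucose, at 3, 6 and 12 months off treatment, with an ECG at 6 months. In the phase I experience reported in Section 1.2, the most common events of grade 3 or worse were thrombocytopenia (9 of 44 patients), neutropenia (3 of 44) and hyperglycemia (3 of 44), all of which these tests can detect. If such a finding were serious, related and already listed in the brochure at that severity, it would be reported to the sponsor and left out of C3D. At stake are the completeness of the late safety data in C3D and their agreement with the SAE reports.

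**Working it through.** No formula applies and the plan gives no figure to reproduce. The check sets the capture rule beside the reporting rule for the same window and follows each kind of serious event through both.

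**Inputs**

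- Window: more than 30 days after the last treatment (6.2.2) or last administration (7.1.1). The two agree.
- C3D rule (6.2.2): serious, unexpected and related.
- Late SAE rule (7.1.1): serious and at least possibly related.
- Meaning of unexpected: 7.1.3.
- Other channels: 6.2.1 (source documents), 7.3 (sponsor), 7.4 (collaborator), 7.2.2 (IRB table).

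**Result for a serious event in the late window**

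| Attribution | Expectedness | C3D under 6.2.2 | Recorded and reported under 7.1.1 |
|---|---|---|---|
| Related | Unexpected | Yes | Yes |
| Related | Expected | No | Yes |
| Possibly related | Unexpected | Unclear: depends on whether 'related' includes 'possibly related' | Yes |
| Possibly related | Expected | No | Yes |
| Unrelated | Either | No | No |

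**Reading the table**

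1. The rules disagree in rows two and four because of expectedness. They may also disagree in row three, because the attribution thresholds are worded differently.
2. For row two, the other channels all take the event: source documents, the sponsor report, the collaborator report and the IRB table. C3D is the only place from which it is missing.
3. No row requires a site to break one rule in order to obey the other. The general statement in 7.1.1 yields to Section 6.2 on the case report form, and the late SAE sentence points to 7.3 and 7.4, which are reporting channels. What remains unclear in that sentence is where 'recorded' applies, since it names no database.
4. Whether a given toxicity falls in row one or row two depends on the brochure, which is not among the documents. A known toxicity that occurs at a greater severity than the brochure lists is unexpected under 7.1.3 and would be captured.

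**The case against.** The strongest reply is that nothing is lost that matters. Section 7.1.1 defers to Section 6.2 on the case report form. The events remain in four other places. No section says that late safety summaries will come from C3D alone. Section 3.3.2 describes marrow suppression with this class of drug as typically transient and reversible, which points to few hematologic events first arising after day 30. Most of this stands. It limits the point to the content of C3D and makes the understatement conditional on summaries being drawn from C3D. It does not remove the mismatch: C3D is the only data collection system the protocol names, and no section says that another source will supplement it.

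A reader might infer three stronger things, none of which the documents support.

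- **That 6.2.2 contradicts 7.1.1.** It does not, for the reason given in step 3 of the working.
- **That thrombocytopenia, diarrhea, hyperglycemia and infection are excluded by definition.** Under 7.1.3 this turns on the brochure's listed specificity and severity, so no toxicity can be declared excluded in advance.
- **That the Section 8 stopping rule is compromised.** Section 8 halts enrollment when, after 6 or more patients, the cumulative fraction with DLTs is 1/3 or greater. Since 6 × 1/3 = 2, the rule can first act at 2 of 6, and Section 3.3.2 says "A DLT-like event will be defined as any of the following AEs occurring at any time". It is tempting to conclude that one uncaptured late event could change the outcome. But Section 8 does not cite the DLT-like definition, which serves to decide dose reduction or discontinuation for the individual patient. Nor does Section 8 say that DLTs are counted from C3D. Under 7.5.1 the principal investigator reviews adverse event data on each patient, and under 7.3 serious events go to the sponsor immediately, so those applying the rule would know of the event anyway. The rule also counts patients, so a late event matters only in a patient without an earlier DLT.

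**Conclusion.** The point holds as a data-capture mismatch of minor severity. More than 30 days after the last treatment, C3D will lack serious related events that are already listed in the brochure at the observed specificity and severity, while the SAE reports will contain them. Any late safety summary built from C3D alone would understate known toxicity and would not reconcile with those reports.

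The size cannot be computed. The documents give no rate of late serious related events, and with an accrual ceiling of 50 patients (Section 8) the count is probably small. The conclusion rests on two assumptions: that at least one such event occurs, and that late safety summaries are drawn from C3D without supplementing them from the SAE reports. The primary response analysis is unaffected, and no effect on the stopping rule is shown.

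**What to change.** Reword Section 6.2.2 so that, in the late window, C3D captures events that are serious and at least possibly related to the treatment. This deletes 'unexpected' and adopts the attribution threshold of 7.1.1, which also settles row three of the table. C3D and the late SAE reports required by 7.1.1 would then hold the same events. The IRB table in 7.2.2, which takes serious events regardless of attribution, would still need the unrelated late ones from another source.

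If the sponsor prefers to leave 6.2.2 as it is, a second-best remedy is a sentence stating that late safety summaries also draw on the SAE reports.

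The cost is one sentence and a few additional C3D entries for events that are already being reported. No new assessment or visit is needed.

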6.2.4 Concomitant medications

Only those medications that the patient is taking at baseline on a routine basis or medications that cause an AE will be captured in C3D. [Thus onetime medications and PRN medications will not be captured in C3D except those used to treat adverse events.]

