11.1.12 Toxicity

Study CUDC-907-101

As of the data cut-off of 02 November 2015, the most frequently reported AEs in CUDC-907-101 have been diarrhea, fatigue, nausea thrombocytopenia, and neutropenia. The frequency and severity of AEs on the 60 mg 5/2 schedule appears comparable to those observed in the overall population of subjects dosed with CUDC-907 on this trial. Additionally, this dose and schedule appears to be better tolerated than the QD dosing schedule (30 or 60 mg), during which all subjects experienced Grade 1-3 diarrhea and Grade 1-4 thrombocytopenia as frequent AEs (50% of subjects on the QD schedule). Among 29 subjects enrolled at the 60 mg 5/2 dosing schedule, diarrhea occurred in 63% of those treated and thrombocytopenia occurred in 24%.

Study CUDC-907-102

Similar to the safety results from Study CUDC-907-101, AEs on the CUDC-907-102 study have generally been self-limiting Grade 1 – 2 events of fatigue, nausea, and diarrhea. Adverse events were reported in 71% of subjects with Grade 3 events occurring in 21% of subjects; there were no Grade 4 or 5 events. The most common AEs were fatigue, nausea, decreased appetite, and abdominal pain. No DLTs have been reported to date.

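### Grade 1 adverse events never enter C3D, so any-grade and Grade 1-2 rates of diarrhea, fatigue and nausea drawn from it will run low and cannot be set against the phase I figures

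*Combined protocol and SAP*

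**What the plan says.** Section 6.1 names the data system: "Data will be collected using the NCI C3D web based data collection system". Section 6.2.1 starts from full capture, under which "all adverse events will be described in the source documents and be reviewed by the designated research nurse, and captured in C3D". Section 6.2.3 then narrows this: "The following Adverse Events will be captured only in the source documents and will not be reported in C3D". The two items listed are laboratory values that do not support a reportable event, and "All grade 1 events". Neither item makes an exception for toxicities already known for this drug.

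Other sections agree with the exclusion. Section 7.1.1 says "All AEs must be recorded on the AE case report form unless otherwise noted above in Section 6.2", and Section 7.2.2 does not ask for Grade 1 events at continuing review.

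The protocol's safety background points to low grades. Table 2 in Section 1.2 pools Grades 1 and 2 in one column. Section 11.1.12 says of the solid-tumor trial that "AEs on the CUDC-907-102 study have generally been self-limiting Grade 1 – 2 events of fatigue, nausea, and diarrhea", and names decreased appetite and abdominal pain among its most common events. For the hematologic trial, the same section gives a diarrhea rate of 63% on the 60 mg 5/2 schedule, without splitting it by grade.

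**The concern.** The rule removes the lowest grade of every adverse event from the trial's database, and the protocol's own data put this drug's main symptomatic harms almost entirely in the two lowest grades. A safety table built from C3D would begin at Grade 2, yet nothing in the protocol says that such tables must be labelled that way.

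If such a table were read as any-grade toxicity, diarrhea, fatigue and nausea would look rarer than they were. Placed beside Table 2 or the 63% in Section 11.1.12, CUDC-907 could look better tolerated in thyroid cancer than in earlier trials purely because of the capture rule. Section 6.3.1 sends results to a public repository, BTRIS and publications, where readers will not have the data-entry rules at hand. Treatment is oral and continues until progression or unacceptable toxicity (Section 3.6.1), so persistent low-grade symptoms matter when tolerability is described.

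**Working it through.** **Inputs** (Table 2, Section 1.2; 44 patients). Diarrhea: 23 at Grade 1-2 and 2 at Grade 3. Fatigue: 16 and 1. Nausea: 11 and 0.

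**Reproducing the printed figures.** 23/44 = 52.3%, 16/44 = 36.4% and 11/44 = 25.0%. These match the printed 52%, 36% and 25%.

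**Share of cases exposed to the rule.** This is the Grade 1-2 count over all cases:
- diarrhea 23/25 = 92%
- fatigue 16/17 = 94%
- nausea 11/11 = 100%

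For contrast, thrombocytopenia is 2/11 = 18% and hyperglycemia 0/3 = 0%. The problem is concentrated in the symptomatic terms.

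**Effect on an any-grade rate from C3D.** Let g be the unknown share of Grade 1-2 patients whose worst grade is 1. Then

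C3D rate = [(1 - g) × (Grade 1-2 count) + (Grade 3 or higher count)] / 44.

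For diarrhea at g = 0.25 this is (0.75 × 23 + 2)/44 = 19.25/44 = 43.8%. The other cells follow in the same way.

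| Event | Grade 1 kept (g = 0) | g = 0.25 | g = 0.50 | g = 0.75 | Limit, g = 1 |
|---|---|---|---|---|---|
| Diarrhea | 25/44 = 56.8% | 43.8% | 30.7% | 17.6% | 4.5% |
| Fatigue | 17/44 = 38.6% | 29.5% | 20.5% | 11.4% | 2.3% |
| Nausea | 11/44 = 25.0% | 18.8% | 12.5% | 6.2% | 0.0% |

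The documents give no value for g, so the three middle columns are an assumed range and the outer columns are the bounds.

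**Does Table 2 count each patient once?** The table's g = 0 column assumes so. For thrombocytopenia, 7 + 2 = 9 agrees with the 9 patients at Grade 3 or worse in the text, and for hyperglycemia 1 + 2 = 3 also agrees. For neutropenia, 2 + 2 = 4, but the text gives 3. Either one patient appears in two columns or one figure is wrong. If both Grade 3 diarrhea patients were also counted in the Grade 1-2 column, the any-grade rate would be 23/44 = 52.3%. The C3D rate would then be (0.75 × 21 + 2)/44 = 40.3%, (0.50 × 21 + 2)/44 = 28.4% or (0.25 × 21 + 2)/44 = 16.5%. The pattern hardly changes.

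**What the rule leaves alone.** Section 8 stops enrollment on the fraction of patients with DLTs. The nearest definition, the DLT-like event in Section 3.3.2, rests on Grade 3 or 4 events or a 21-day dose delay. The primary endpoint is RECIST response. None of these uses Grade 1 entries.

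**The case against.** The best defense is that the exclusion is deliberate and that no planned analysis depends on it. This is largely right. Sections 6.2.3, 7.1.1 and 7.2.2 are consistent with one another. The objectives are response, survival and biomarkers. Section 8 plans no any-grade toxicity estimate and no comparison of adverse event rates with phase I, whose data serve to choose the dose and schedule. A table correctly labelled as Grade 2 and higher would not be biased. The comparison with Table 2 is also imperfect for other reasons: only 7 of its 44 patients were on the 5/2 schedule, and they had lymphoma or myeloma.

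What survives is narrower. The protocol does not require that label, and the rates most likely to be quoted for this drug are the ones the rule lowers.

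A reader might infer more, but the documents do not carry it:

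- *That Grade 1 data are lost, or that nothing can be compared with phase I.* The events stay in nurse-reviewed source documents, and Grade 3 and higher rates can still be set against Table 2.
- *That early antidiarrheal use pushes cases out of the database.* Section 4 says "Antidiarrheal treatment (e.g., loperamide) will be administered immediately upon the first onset of symptoms". An effect that holds cases at Grade 1 is plausible, but it is stated nowhere.
- *That loperamide will appear in C3D without a matching event.* Section 6.2.4 says "onetime medications and PRN medications will not be captured in C3D except those used to treat adverse events". This could refer to any adverse event or only to those entered in C3D, so a mismatch is possible but not established.
- *That a later trial would inherit wrong rates.* Section 10.5 makes a larger trial conditional on tumor response, not on toxicity rates.

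**Conclusion.** The concern holds in limited form. Any-grade and Grade 1-2 rates of diarrhea, fatigue and nausea taken from C3D will be understated whenever some patients' worst grade is 1. They cannot be set against Table 2's pooled column, nor against the 63% diarrhea rate in Section 11.1.12 if that figure covers all grades, as its presentation suggests.

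The direction is certain but the size is not. With a phase I-like profile, each patient counted once and a Grade 1 share of 25% to 75%, diarrhea would read about 44% to 18% instead of 57%, fatigue 30% to 11% instead of 39%, and nausea 19% to 6% instead of 25%.

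It would be wrong to conclude that the safety monitoring or the trial's main result is compromised: Grade 3 and higher rates, the DLT stopping rule and the primary endpoint stand as they are. The weakness is in how low-grade tolerability will be described. It is worth correcting because the correction is cheap.

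**What to change.** In Section 6.2.3, replace "All grade 1 events" with: *Grade 1 events other than diarrhea, fatigue, nausea, decreased appetite and abdominal pain*. These are the common symptomatic terms that Table 2 and Section 11.1.12 name between them. Enter the Grade 1 events for these five terms from the source documents into C3D.

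In the safety tables, report each patient's worst grade. For the five terms, show Grade 1 and Grade 2 separately, plus a combined Grade 1-2 column that can be set beside Table 2. Label every other term as Grade 2 and higher only.

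Laboratory terms need not be added. Table 2 has no Grade 1-2 hyperglycemia and only 2 Grade 1-2 cases each of thrombocytopenia and neutropenia, and the separate laboratory exclusion in Section 6.2.3 would also have to be amended.

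The cost is an amendment and modest data entry for five terms in at most 50 patients, the accrual ceiling in Section 8. The events are already recorded and reviewed, so no new assessment is needed, and no dose or clinical rule changes. The reported any-grade rates will be higher, and so less favorable to the drug.
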